5.4. Screen Failures

Since this is an open-label long-term continuation study for participants who have completed other qualifying studies, eg, Protocol C0251002, screen failures are not applicable.

6. STUDY INTERVENTION(S) AND CONCOMITANT THERAPY

Study intervention is defined as any investigational intervention(s), marketed product(s), placebo, medical device(s), or study procedure(s) intended to be administered to a study participant according to the study protocol.

For the purposes of this protocol, study intervention refers to PF-06823859.

6.1. Study Intervention(s) Administered

For this study, the study intervention will be administered intravenously over approximately one hour. Study intervention will be administered every 4 weeks, each participant receiving 13 doses of study intervention over the duration of the trial.

Study Interventions(s)	
Intervention Name	PF-06823859
ARM Name (group of patients receiving a specific treatment (or no treatment)	PF-06823859
Type	Drug
Dose Formulation	Solution for injection
Unit Dose Strength(s)	100 mg/mL
Dosage Level(s)	600 mg Q4W
Route of Administration	IV
Use	Experimental
IMP or NIMP	IMP
Sourcing	Provided centrally by the sponsor or locally by the trial site, subsidiary, or designee. See IP manual for more information.
Packaging and Labeling	Open-label study intervention will be provided in a 6 mL glass vial sealed with a stopper and aluminum flip off cap. Each vial contains 1.35 mL PF-06823859. The vials will be packaged into cartons containing 6 vials per carton. Each vial and carton will be labeled as required per country requirement.

6.1.1. Administration

Open-label IV PF-06823859 will be administered at the investigative site or clinic over the course of approximately 60 minutes as an IV infusion, using a calibrated infusion pump. Once the infusion has completed, all participants will be monitored for an additional 60 minutes post study intervention administration to ensure no infusion site reactions.

6.1.1.1. Infusion Discontinuation

- If a participant experiences symptoms typical of an allergic reaction, the study intervention administration should be discontinued immediately and permanently and the event should be captured as an AE.

- If a participant experiences symptoms typical of infusion reactions (eg, lightheadedness, nausea, chills, fever), the study intervention infusion should be stopped. At the discretion of the investigator, the infusion can be restarted at a slower rate if symptoms are resolved within 1 hour after the stop of infusion. If symptoms return, then the study intervention administration should be discontinued immediately and permanently.
- In the event that there is an infusion interruption, the entire duration of drug infusion, from the initial start of infusion to the completion of infusion, should not exceed 3 hours. Participants will receive appropriate treatment at the discretion of the investigator.

6.1.1.2. Pre-Medication Use on the Day of IVIG Administration

For participants who enroll in the study who are receiving IVIG: On the day of IVIG dose administration, pre-medication to prevent hypersensitivity reaction to IVIG is permitted. The steroid dose that was previously used for pre-medication will be permitted (on IVIG dosing day only). After IVIG dosing day, steroid dosing should remain less than or equal to 15 mg or equivalent of prednisone per day for participants in the severe skin disease cohort and 20 mg or equivalent of prednisone per day for participants in the moderate muscle disease cohort as per protocol [Section 6.8.3](#).

There is no need to change the IVIG dosing schedule or adjust the IVIG dosing schedule related to study intervention administration.

6.2. Preparation, Handling, Storage, and Accountability

1. The investigator or designee must confirm appropriate temperature conditions have been maintained during transit for all study interventions received and any discrepancies are reported and resolved before use of the study intervention.
2. Only participants enrolled in the study may receive study intervention and only authorized site staff may supply or administer study intervention. All study interventions must be stored in a secure, environmentally controlled, and monitored (manual or automated recording) area in accordance with the labeled storage conditions with access limited to the investigator and authorized site staff. At a minimum, daily minimum and maximum temperatures for all site storage locations must be documented and available upon request. Data for nonworking days must indicate the minimum and maximum temperatures since previously documented for all site storage locations upon return to business.
3. Any excursions from the study intervention label storage conditions should be reported to Pfizer upon discovery along with any actions taken. The site should actively pursue options for returning the study intervention to the storage conditions described in the labeling, as soon as possible. Once an excursion is identified, the study intervention must be quarantined and not used until Pfizer provides permission to use the study intervention. Specific details regarding the definition of an excursion

and information the site should report for each excursion will be provided to the site in the IP manual.

4. Any storage conditions stated in the SRSD will be superseded by the storage conditions stated on the label.
5. Study interventions should be stored in their original containers.
6. The investigator, institution, or the head of the medical institution (where applicable) is responsible for study intervention accountability, reconciliation, and record maintenance (ie, receipt, reconciliation, and final disposition records), such as the IPAL or sponsor-approved equivalent. All study interventions will be accounted for using a study intervention accountability form/record.
7. Further guidance and information for the final disposition of unused study interventions are provided in the IP manual. All destruction must be adequately documented. If destruction is authorized to take place at the investigator site, the investigator must ensure that the materials are destroyed in compliance with applicable environmental regulations, institutional policy, and any special instructions provided by Pfizer.

Upon identification of a product complaint, notify the sponsor within 1 business day of discovery as described in the IP manual.

6.2.1. Preparation and Dispensing

A qualified staff member will dispense the study intervention using the IRT system via unique container numbers in the single-use vials provided, in quantities appropriate according to the dose assignment.

See the IP manual for instructions on how to prepare the study intervention for administration. Study intervention should be prepared and dispensed by an appropriately qualified and experienced member of the study staff (eg, physician, nurse, physician's assistant, nurse practitioner, pharmacy assistant/technician, or pharmacist) as allowed by local, state, and institutional guidance. A second staff member will verify the dispensing.

PF-06823859 be prepared by qualified site personnel according to the IP manual. The study intervention will be administered in an open-label fashion to the participants.

6.2.2. Study Intervention Accountability

The investigator site must maintain adequate records documenting the receipt, use, loss, or other disposition of the study intervention supplies. All study intervention will be accounted for using a drug accountability form/record.

6.2.2.1. Destruction of Study Intervention Supplies

The sponsor or designee will provide guidance on the destruction of unused study intervention (eg, at the site). If destruction is authorized to take place at the investigator site, the investigator must ensure that the materials are destroyed in compliance with applicable environmental regulations, institutional policy, and any special instructions provided by Pfizer, and all destruction must be adequately documented.

All used glass vials should be maintained at the investigative site for accountability. The investigator will maintain the unused supply until destruction is authorized. Pfizer will provide instructions as to the disposition of any unused study intervention.

6.3. Measures to Minimize Bias: Randomization and Blinding

6.3.1. Allocation to Study Intervention

Study intervention will be administered at the study visits summarized in the [SoA](#).

This is an open-label study. The site will contact the IRT prior to the start of study intervention administration for each participant. The site will record the vial numbers assigned on the applicable CRF, if required.

The investigator's knowledge of the treatment should not influence the decision to enroll a particular participant or affect the order in which participants are enrolled.

6.4. Study Intervention Compliance

Participants will receive study intervention directly from the investigator or designee, under medical supervision. The date and time of each dose administered in the clinic will be recorded in the source documents and recorded in the CRF. The dose of study intervention and study participant identification will be confirmed at the time of dosing by a member of the study site staff other than the person administering the study intervention.

The site will complete the required dosage Preparation Record located in the IP manual. The use of the Preparation Record is preferred, but it does not preclude the use of an existing appropriate clinical site documentation system. The existing clinical site's documentation system should capture all pertinent/required information on the preparation and administration of the dose. This may be used in place of the Preparation Record after approval from the sponsor and/or designee.

6.5. Dose Modification

Dose modification is not permitted in this study.

6.6. Continued Access to Study Intervention After the End of the Study

No intervention will be provided to study participants at the end of their study participation.

6.7. Treatment of Overdose

For this study, any dose of PF-06823859 greater than 600 mg within a 24-hour time period will be considered an overdose.

There is no experience with overdose of PF-06823859. There is no specific antidote for overdose with PF-06823859. Treatment at the discretion of the investigator should be symptomatic and supportive. In case of an overdose, it is recommended that the subject be monitored for signs and symptoms of adverse reactions. Participants who develop adverse reactions should receive appropriate treatment.

In the event of an overdose, the investigator/treating physician should:

1. Contact the medical monitor within 24 hours.
2. Closely monitor the participant for any AEs/SAEs and laboratory abnormalities for at least 5 half-lives or 28 calendar days after the overdose of PF-06823859 (whichever is longer). Closely monitor the participant for any AEs/SAEs.
3. Document the quantity of the excess dose as well as the duration of the overdose in the CRF.
4. Overdose is reportable to Pfizer Safety only when associated with an SAE.
5. Obtain a blood sample for PK analysis within 1-2 days from the date of the last dose of study intervention if requested by the medical monitor (determined on a case-by-case basis).

Decisions regarding dose interruptions or modifications will be made by the investigator in consultation with the medical monitor based on the clinical evaluation of the participant.

6.8. Concomitant Therapy

Hormonal contraceptives that meet the requirements of this study are allowed to be used in participants who are WOCBP (see [Appendix 4](#)).

For a list of prohibited and permitted concomitant medications refer to [Appendix 8](#) ([Section 10.8](#)).

All ongoing medications from the previous study should be re-written in the new concomitant medication page for this study.

Participants must continue to avoid use of medications that have been washed out prior to enrollment in their prior qualifying study (eg, C0251002 Protocol). The indication for use, total daily dose, route of administration, and start and stop dates for all ongoing medications (including prescription medications and treatments, vaccinations, nonprescription medications, nondrug treatments and dietary supplements) will be pulled from the qualifying study and documented as prior medications.

Participants will be asked about all concomitant treatments (including prescription medications and treatments, vaccinations, nonprescription medications, nondrug treatments, dietary supplements, and herbal preparations) at each study visit. Medications after the first dose of study intervention has been administered in this OLE study will be documented as concomitant medications. Any new concomitant medications or dose changes to current concomitant medications should be evaluated for potential new or worsening AEs.

For the purposes of this protocol, dietary supplements are defined as vitamins, minerals, purified food substances, and herbals with pharmaceutical properties. Vitamins, minerals, purified food substances, and herbals with pharmaceutical properties are allowed in amounts not known to be associated with adverse effects (such as hypervitaminosis).

6.8.1. Prohibited Concomitant Medications

Please see [Appendix 8, Section 10.8](#).

6.8.2. Permitted Concomitant Medications

NSAIDs and aspirin are allowed; however, they may potentially affect efficacy parameters (eg, the skeletal disease activity VAS, arthritis assessment and gastrointestinal disease activity VAS for the MDAAT and thus should be used judiciously. Participants taking NSAIDS/analgesics should not take a dose of these medications within 12 hours prior to such assessments at those visits.

Acetaminophen is primarily an analgesic and lacks the anti-inflammatory properties of NSAIDS. The use of acetaminophen is recommended when possible to treat non-DM related conditions, in the absence of a pre-existing hepatic function deficiency.

6.8.3. Corticosteroids

Please refer to [Appendix 11, Section 10.11](#).

The decision for increasing or tapering steroids is entirely up to the study investigator, and any change in the steroid dose should be recorded on the concomitant medication page.

All concomitant treatments including corticosteroids or equivalent taken during the study must be recorded in study records with indication for use, total daily dose, and start and stop dates of administration.

Oral corticosteroids taken by the participants during the study will be captured on a separate CRF. The CRF page will capture the name of the corticosteroid taken, indication for use, total daily dose, route of administration, and start date and stop dates of administration.

6.8.3.1. Guidance for Investigators

During the course of the study, those participants who experience a severe flare requiring new or increased doses of immunosuppressants (including new or increased doses of corticosteroids beyond what is permitted), will be discontinued from the treatment period of the study and placed in the follow up period, and therefore, will receive no further study intervention. Rescue therapy may be administered as clinically necessary.

See [Appendix 11 \(Section 10.11\)](#) for further guidelines for corticosteroid use.

6.8.4. Rescue Medicine

If the participant requires the addition of higher DMARD doses or an additional DMARD for a flare or persistent increase in dermatomyositis activity, then the participant should be discontinued from the treatment period but complete the follow-up visits. High dose oral corticosteroids (>100 mg/day prednisone, or equivalent) or pulse IV doses, or any IV or IM steroid injection would exclude the participant for further treatment in the study.

See [Appendix 11 \(Section 10.11\)](#) for further guidelines for rescue medication.

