10.8. Appendix 8: Permitted and Prohibited Concomitant Medications

The prohibited concomitant medications listed below (Table 4) should not be taken during the C0251008 study.

The Pfizer study team is to be notified of any prohibited medications taken during the study. After consulting with the sponsor, the investigator will make a judgement on the ongoing participation of any participant with prohibited medication use during the study.

This list of drugs prohibited for potential DDI concerns with the IMP may be revised during the course of the study with written notification from the sponsor, to include or exclude specific drugs or drug categories for various reasons (eg, emerging DDI results for the IMP, availability of new information in literature on the DDI potential of other drugs).

This is not an all-inclusive list. Site staff should consult with the sponsor or designee with any questions regarding potential DDI.

Table 4. List of Prohibited and Permitted Concomitant Medications

Medications		C0251008 Treatment Period Day 1-Week 52	C0251008 Follow-up Period
Corticosteroids	Parenteral injections (intra-articular) IA, IM, or IV)	Prohibited	Permitted
	Oral (prednisone or equivalent)	
Permitted (Stage 2)
 
Prednisone \leq15 mg/day or equivalent provided dose is stable for at least 30 days prior to Day 1. 
Permitted (Stage 3)
 
Prednisone \leq20 mg/day or equivalent provided dose is stable for at least 30 days prior to Day 1.Tapering of steroids is permitted after Week 52, in Amended Stage 2 and Stage 3.	Permitted
Immunosuppressive or immunomodulatory agents including methotrexate (MTX), azathioprine (AZA), leflunomide, mycophenolate (including mycophenolate mofetil, mycophenolate mofetil hydrochloride, and mycophenolate sodium), or 6-mercaptopurine (6-MP).		
Permitted
 
Provided pre-existing dose is stable for at least 60 days prior to Day 1.No new immunosuppressives or increase in dose is allowed during the treatment period.Participants can be on 1 of the following cytotoxic agents: MTX, AZA, leflunomide, mycophenolate, or 6-MP, but not on any combination of these cytotoxic agents.	Permitted
Antimalarials (eg, hydroxychloroquine, chloroquine, quinacrine)		
Permitted
 
Provided pre-existing dose is stable for at least 60 days prior to Day 1.	Permitted

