10.11.2. Corticosteroid Rescue Guidance

10.11.2.1. Oral or Intramuscular Corticosteroid Rescue Recommended Guidance for Dermatomyositis Related Reasons

Systemic corticosteroids may be increased as clinically required; however, are suggested to remain within the following stipulations as a guidance.

Recommended Oral or Intramuscular corticosteroid rescue therapy:

- Two of the following options, or the same option used twice are allowed at any time, except between Week 44 and Week 52 due to final assessments being completed.
- Each event of corticosteroid rescue is recommended to be recorded on the concomitant medication pages (All doses are approximate as these are examples only):
 1. Increase in oral corticosteroid dose up to the participant's baseline dose (dose at Day 1). Consideration can then be given to following the protocol driven corticosteroid recommended taper.
 2. Increase in oral corticosteroid dose up to 20 mg of prednisone equivalent per day. Consideration can then be given to following the protocol driven corticosteroid recommended taper.
 3. Oral corticosteroid taper of 20 mg prednisone equivalent per day of over 1 month can be given on top of the baseline corticosteroid dose.

Recommended taper on top of the baseline dose as follows: 20 mg prednisone equivalent per day for 1 week, then 15 mg per day for 1 week, then 10 mg per day for 1 week, then 5 mg per day for 1 week, then back to baseline corticosteroid dose. Consideration can then be given to following the protocol driven corticosteroid recommended taper.

4. An intramuscular injection of approximately 40 mg Depo-Medrol (methylprednisolone acetate suspension [50 mg prednisone equivalent]) as an example. Consideration can then be given to following the protocol driven corticosteroid recommended taper.

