10.11.2.3. Intra-Articular Corticosteroids

A participant who receives an intra-articular steroid injection will be allowed to continue in the treatment period of the trial. However, it is preferable to have an intra-articular corticosteroid injection >30 days before the clinical efficacy assessment visit.

A participant who receives an intra-articular corticosteroid injection within 30 days of when efficacy assessments are performed will need to complete the efficacy assessments.

10.11.2.4. Immunosuppressives/immunomodulatory Agent Rescue Medications.

A participant who requires an increase or additional non-steroid immunosuppressive/immunomodulatory agent, including prohibited medications, will be withdrawn from the treatment period and enter the follow-up period of the trial.

However, if there is a requirement for a decrease in a non-steroid immunosuppressive/immunomodulatory agent for a safety or a tolerability issue, then this may be allowed after a discussion with the medical monitor and should be documented.

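### The protocol contradicts itself on whether an intramuscular or intra-articular steroid injection ends study treatment, and the passage a site follows decides which CDASI, TIS and CSM scores are analysed

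*Protocol*

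**What the plan says.** **Passages under which treatment stops.** Protocol 6.8.4 states: "pulse IV doses, or any IV or IM steroid injection would exclude the participant for further treatment in the study". Table 4 in Appendix 8 has a row for "Parenteral injections (intra-articular) IA, IM, or IV" and marks it prohibited through the treatment period (Day 1 to Week 52). Section 7.1 lists use of prohibited medication among the reasons for permanently stopping study intervention, and Appendix 10 (10.10.2) makes stopping mandatory for it.

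**Passages under which treatment continues.** Section 6.8.4 itself sends the reader to Appendix 11 "for further guidelines for rescue medication". Section 10.11.2.1 there lists, as its fourth rescue option, "An intramuscular injection of approximately 40 mg Depo-Medrol". The timing rule is "Two of the following options, or the same option used twice are allowed at any time, except between Week 44 and Week 52". The section introduces its limits as ones that "are suggested to remain within the following stipulations as a guidance". On IA injections, Section 10.11.2.3 says: "A participant who receives an intra-articular steroid injection will be allowed to continue in the treatment period of the trial". It adds that a participant injected "within 30 days of when efficacy assessments are performed will need to complete the efficacy assessments".

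**A third position.** The text of Appendix 8 leaves ongoing participation after prohibited medication to the investigator's judgement, after consulting the sponsor. Appendix 10 cites that same appendix when it makes stopping mandatory.

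**Analysis rules.** Protocol 9.1.1.2 sets scores after treatment withdrawal to missing for E1 and E2. SAP 6.2.1.1 (CDASI), 6.2.2.1 (TIS) and 6.2.3.1 (CSMs) exclude data after study drug discontinuation. The only intercurrent event named in the estimands is study withdrawal. Steroid rescue is not named.

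**The concern.** The same injection ends dosing under one set of passages and can leave the participant on study drug under the other. Because score exclusion is tied only to discontinuation, this one decision also fixes whether the participant's later scores, including Week 52, enter the analysis. If sites read the protocol differently, the CDASI estimates in both cohorts, and the TIS and CSM estimates in the Muscle Analysis Set, mix participants whose identical events were handled in opposite ways.

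More than efficacy is at stake. The primary objective is long-term safety, and the conflict changes how much study drug a participant receives. Membership of the safety sets is unaffected, and SAP 6.1.1 excludes safety data only after study withdrawal.

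**Working it through.** The plan gives no figure to reproduce, so the check is a comparison of texts followed by a count of what depends on the reading.

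**Intra-articular.** Table 4 prohibits it, Appendix 10 requires stopping for prohibited medication, and Section 10.11.2.3 says the participant goes on. That last statement is not worded as a suggestion. The conflict is explicit. (Section 6.8.4 names only IV and IM, so it is not part of the IA conflict.)

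**Intramuscular.** Section 6.8.4 and Table 4 are rules. Appendix 11 does not say in words that dosing continues after an IM injection, but three features imply it:

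- Avoiding Weeks 44 to 52 because of the final assessments presupposes someone still on treatment.
- So do a permitted second use and a return to the steroid taper.
- Section 10.11.2.4 spells out withdrawal from treatment, but only for non-steroid agents.

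**Count of doses and assessments.** Inputs:

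- Doses every 4 weeks from Day 1 to Week 48 (Tables 1 and 2): 48/4 + 1 = 13.
- Post-baseline CDASI in the treatment period, both schedules: Weeks 12, 24, 36, 48 and 52, so 5.

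Assume the injection comes just after the dose at week w (Day 1 = 0), and the visit's assessment precedes the dose. If treatment then stops:

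- doses received = w/4 + 1; doses lost = 13 − (w/4 + 1)
- assessments kept = number of {12, 24, 36, 48, 52} that are ≤ w; assessments lost = 5 − kept

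| Injection just after dose at | Doses received | Doses lost | CDASI kept | CDASI lost |
|---|---|---|---|---|
| Day 1 | 1 | 12 | 0 | 5 |
| Week 12 | 4 | 9 | 1 | 4 |
| Week 24 | 7 | 6 | 2 | 3 |
| Week 36 | 10 | 3 | 3 | 2 |
| Week 40 | 11 | 2 | 3 | 2 |
| Week 48 (IA only) | 13 | 0 | 4 | 1 |

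Week 40 is the last dose before the Week 44 to 52 exception. For IM, therefore, the two readings differ by 12 down to 2 doses and by 5 down to 2 assessments, and Weeks 48 and 52 are always among those lost. Section 10.11.2.3 sets no such exception for IA, so the IA range runs down to 0 doses and 1 assessment (Week 52).

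**Weight of one participant.** The documents expect about 30 participants in total and give no split. Assuming 10 to 20 per cohort, one participant is 1/20 = 5% to 1/10 = 10% of that cohort's Week 52 data.

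**Does Section 10.11.2.2 help?** For steroids given for reasons other than dermatomyositis near the end, it moves efficacy assessments to the first follow-up visit, which is Week 56 in the schedules. SAP 9.1 sets Week 52 as Days 362–368 and Week 56 as Days 390–396. The gap is 390 − 368 = 22 days, and SAP 5.2.1 fits the model only to Week 52. A moved score would not enter as Week 52. As extracted, Tables 1 and 2 schedule no CDASI at Week 56; the next is Week 60.

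**The case against.** The strongest objection is that the IM conflict is softer than the IA one. Appendix 11 words its limits as guidance and its doses as examples, and Section 6.8.3.1 shows that rescue can accompany stopping. The rule in 6.8.4 could then simply prevail. The difference in strength is real. But it does not resolve the conflict: 6.8.4 points to Appendix 11 without stating precedence, and the timing exception makes little sense for someone already off treatment.

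Other points stand in part:

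- The counts ignore the Early Termination visit, which includes CDASI. The documents do not say whether that score counts as after discontinuation, so the kept counts could rise by one.
- Oral rescue also produces on-treatment scores after rescue. Reconciling the injection rules would not settle how those are handled, so the SAP needs its own statement.
- The Appendix 8 text on ongoing participation may mean study participation rather than treatment. That third conflict is the least direct.
- Efficacy is secondary, with no tests or p-values. The sponsor's team must be told of prohibited medication, which should limit divergence between sites, though it has no single rule to apply. Stopped participants remain in safety follow-up.

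These limit the statistical damage. None of them makes the two sets of passages compatible.

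**Conclusion.** The concern holds and must be fixed. The protocol gives incompatible instructions for an IA injection explicitly, and for an IM injection by clear implication. Because E1, E2 and the SAP tie exclusion only to discontinuation, the choice carries through to the analysed data.

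For IM, the readings differ by between 2 and 12 of 13 doses and between 2 and 5 of 5 treatment-period CDASI assessments, depending on timing. For IA, the lower ends are 0 doses and 1 assessment. The Week 52 score is in dispute in every case. These counts assume the participant would otherwise complete the schedule, the assessment precedes the dose, and the Early Termination score is not used. The shift in the estimated means cannot be given, since the documents state neither a rescue rate nor a rescue effect.

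**What to change.** 1. **Protocol.** Reconcile Sections 6.8.3.1, 6.8.4 and 7.1, Appendix 8 with Table 4, Appendix 10 and Appendix 11 into one consistent rule on what each route of steroid injection means for further study treatment. Section 6.8.3.1 belongs on the list because it turns on steroid doses beyond those permitted, which depends on the passage read. The clinical content is for the sponsor to decide.
2. **SAP.** State how scores after on-treatment steroid rescue, by any route, are handled under E1 and E2, and to which visit a score moved under Section 10.11.2.2 is assigned. State also whether an Early Termination score counts as after discontinuation.
3. **Optional.** Add a supplementary analysis that sets scores after rescue to missing, and a summary of steroid use by visit, cohort and route. SAP 6.5.4 plans listings only.

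**Cost.** A protocol amendment needs IRB/EC approval and, if substantial, health authority approval (Protocol 10.1.1), plus SAP text. Items 1 and 2 need no new data. Oral steroids have their own CRF and other steroids go on the concomitant medication pages. For the summary by route, confirm that those pages record route, since Section 6.8.3 lists it only for the oral CRF. The supplementary analysis would add missing data in small cohorts.
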